#### Cost-effectiveness

Procedural costs for intervention and control treatment will be recorded. Procedural costs of admissions for reoperations will also be collected from all units. This allows for basic health economic calculations using Markov modelling.

DAICY Version No: 1.0 Date: 2021-11-17

## 7. STATISTICS

Sample size calculation

Power was calculated for the proposed trial design and primary analysis using simulation. In addition to the hypothesized intervention effect, the power depends on the number of clusters, the number of yearly operations at each cluster, the PJI frequency in the control group, and intracluster and intra-cluster-period correlation.

10000 data sets were randomly generated from a model with individual outcome probabilities

 $logit(Pr{Y_{ijk}=1|c_i, p_{ij}}) = \mu + \beta_{\tau}\tau_{ij} + \beta_{\pi}\pi_j + c_i + p_{ij},$ 

where  $Y_{ijk}$  is the indicator for PJI in patient *k* in period *j* in cluster *i*,  $\tau_{ij}$  indicates DIAC treatment in cluster *i* in period *j*, and  $\pi_j$  is the period indicator. For each simulated data set, the cluster and cluster-period effects  $c_i$  and  $p_{ij}$  were sampled from normal distributions with variance selected to provide the assumed intra-cluster and intra-cluster-period correlations. The overall period effect  $\beta_{\pi}$  is unimportant for the purpose of the simulations and was set to 0, and the intercept  $\mu$  and treatment effect  $\beta_{\tau}$  were set to provide the assumed control and intervention arm outcome probabilities.

The updated simulation model includes the 15 verified participating hospitals, using their recorded yearly number of operations for 2019 (64, 132, 209, 294, 224, 97, 67, 144, 71, 45, 32, 94, 97, 112, and 65). Hence the 4-year trial is assumed to include 7,000 patients in total.

The 1-year risk of PJI in the included population is assumed to be 3% in the control group. This estimate is based on the observed PJI frequency in Sweden (25, 26), and assumed to be conservative. Power was calculated under the hypothesis of 1.5% 1-year risk of PJI in the intervention group will be considered the minimal clinically significant difference motivating a general change in routines and recommendations from single-impregnated antibiotic-loaded cement to DIAC.

Unfortunately, there is no available data to estimate intra-cluster and intra-cluster-period correlations in PJI. For this reason, we simulated power under 3 scenarios; small correlations (0.01 within cluster and 0.008 within cluster-period), medium correlations (0.05 and 0.04 respectively), and large correlations (0.1 and 0.08 respectively), see (27). Under these scenarios, the power to obtain a 2-sided p<0.05 for the hypothesis of no difference was found to be 90%, 86% and 80%, respectively.

#### 7.1. Statistical analysis

Generally, all statistical analyses will account for the cluster-randomized crossover design to ensure correct type I error rates and confidence intervals (CIs). Analyses will be performed using the intention-to-treat principle including all eligible patients with available follow-up data within a study site according to allocated treatment for the study site. The threshold of statistical significance will be set at a 2-sided p-value of 0.05.

As primary analysis, the difference in risk of PJI after the intervention treatment compared to the control group will be estimated using linear regression for aggregated cluster-period data, with proportion of events within a cluster period as dependent variable and treatment, cluster, period

	DAICY	
Clinical Study Protocol	Version No:	1.0
	Date:	2021-11-17

and proportion of females within the cluster period as independent variables. Estimated difference in risk with 95% confidence interval and 2-sided p-value will be presented.

With the registry-based follow-up we assume that follow-up will be complete and the quality of data adequate with confirmation of data in an individual medical charts review. In the rare case that a patient has incomplete follow-up and a value for primary outcome is missing the patient will be excluded from analysis. Death before PJI will be handled as no PJI.

Secondary event outcomes will be analyzed and described in the same way as for the primary outcome.

Supplementary and sensitivity analyses will be performed for all event endpoints. An analysis of the primary outcome including all ITT patients will be performed using multiple imputation for individual outcomes based on individual patient characteristics, details to be described in the Statistical Analysis Plan. Sensitivity analyses to investigate the impact of handling death as non-event, in addition to analyzing death as a secondary outcome, will include analyses of the composite of PJI and death. As a sensitivity analysis for the asymptotic approximation in the linear model, a 2-sided p-value for no difference in proportion will be obtained by Monte Carlo randomization inference based on the likelihood ratio.

As a supplementary analysis, treatment contrasts as odds ratios will be presented for all event outcomes, with 95% confidence intervals. An appropriate method, accounting for the cluster-crossover design, will be pre-defined in the Statistical Analysis Plan. Note that while the linear model for aggregated data, used for the primary analysis, is often robust, asymptotic tests based on other models have a risk of inflated Type I error rates when the number of clusters is small (29). For mortality, an additional supplementary analysis of time-to-event will be performed, using a method accounting for the cluster-allocated crossover design.

Allocated and actual performed treatments will be described in a CONSORT diagram, and additional per-protocol analyses will be undertaken as sensitivity analyses. Secondary outcomes will be presented without formal multiplicity adjustment. A detailed statistical analysis plan will be completed before data base lock.

For all event outcome variables, pre-defined subgroup/interaction analyses to assess the homogeneity of the treatment contrast will be performed, for sex, age, ASA class (I-II or III-IV) and for the procedural characteristics type of stem, head and surgical approach. For categorical subgroup indicators, events will be described in each subgroup as for the entire population, and the treatment contrast in each subgroup will be estimated using a linear model at the cluster level, with proportions summarized by cluster period and subgroup indicator as dependent variable, including treatment, cluster, period and subgroup and interaction between treatment and subgroup as independent variables, and presented with nominal 95% CI for each subgroup and the interaction p-value.

For health economic studies, analyses of cost per quality-adjusted life year will be described in a separate analysis plan.

Data Management

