## 3. STUDY DESIGN AND PROCEDURES

#### 3.1. Overall study design and flow chart

The proposed study is designed as a prospective register-based cluster randomized cross-over study design. The study will be pragmatic, with broad eligibility criteria, participant inclusion by treating department (site), and great freedom for surgeons to choose between different implant brands, surgical approaches and post-operative regimes.

Two thirds of Swedish patients 60 years and above with a displaced femoral neck fracture receive a cemented HA. 2230 procedures were registered in the SFR during 2019 and were eligible for inclusion in the present study.

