## 4. STUDY POPULATION

#### 4.1. Inclusion criteria

- Age ≥60 years
- Diagnosis: displaced femoral neck fracture type AO 31-B2 or B3/Garden type 3 or 4
- Eligible for HA according to local guidelines and routines

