#### 4.3. Subject enrolment and randomization

In the first step of the study, the orthopedic departments included are randomized to start with either the control or intervention treatment. After the first period of 2 years is completed, the study site will change to use the other treatment for the patients included in the following period of 2 years. At each department, information regarding the study is made available on the official web page, the orthopedic ward and the outpatient department. All patients admitted and fulfilling the inclusion criteria and registered in the SFR or SAR will be included. After the index surgery, procedural details and patient characteristics will be collected within the SAR. Procedural details include type and brand of implant, type of components (uni- or bipolar head), type of cement (intervention: DIAC or control: Single-impregnated antibiotic-laden bone cement), surgical approach and type of antibiotic prophylaxis. Patient characteristics registered in the SAR include indication for surgery, age, sex, American Society of Anesthesiologists (ASA) grade and body mass index (BMI). Data on revision surgery performed and on reoperations are registered in the SAR. Data on reoperations are also registered in the NPR. Mortality data are automatically available within the SFR and SAR from the SDR.

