#### 5.2. Blinding

There will no blinding of the bone cement for the surgeon.

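### Open two-year allocation with locally judged eligibility leaves room for selection by infection risk, and a primary model that adjusts patient mix only for sex would not correct it

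*Protocol*

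**What the plan says.** **Allocation.** Departments are randomised to a sequence of two 2-year periods. Under section 4.3, after the first period "the study site will change to use the other treatment for the patients included in the following period of 2 years". Section 5.2 adds: "There will no blinding of the bone cement for the surgeon".

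**Entry.** Section 4.1 requires a displaced femoral neck fracture, age 60 or over, and that the patient is "Eligible for HA according to local guidelines and routines". Section 4.3 includes every admitted patient who meets the criteria and is registered. Section 9.2 asks for no written individual consent.

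**Primary model.** Section 7.1 specifies linear regression on aggregated data, "with proportion of events within a cluster period as dependent variable and treatment, cluster, period" "and proportion of females within the cluster period as independent variables". Analysis follows the treatment allocated to the site.

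**Data at hand.** Section 4.3 lists age, sex, ASA grade and BMI among the registered patient characteristics. In section 7.1, age and ASA class appear only as subgroup factors.

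**The concern.** Randomising whole departments protects the sequence but does not conceal the cement from the person who judges the individual patient. For two years at a time, the cement that the next patient will receive is known. Whether a patient counts as a hemiarthroplasty candidate is a local judgement, so it could in principle drift with the cement in use.

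If higher-risk patients were under-represented in a hospital's control periods, the control risk would fall and a real benefit would be understated. If they were under-represented in its dual-cement periods, a benefit would be overstated or created. Age, ASA grade and BMI are plausible markers of infection risk. They are registered but do not enter the primary model.

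**Working it through.** **1. The plan's own power.** The 15 yearly volumes in section 7 sum to 1,747, and 4 × 1,747 = 6,988, which agrees with 7,000. There are 30 cluster-period proportions. The model has 15 cluster parameters plus period, treatment and proportion of females, 18 in all, which leaves 12 residual degrees of freedom. I simulated the section 7 logit model at 3% against 1.5% (20,000 data sets per scenario, unweighted regression). The larger of each pair of correlations was read as within-period and the smaller as between-period, on the logit scale. That reading is an assumption.

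| Correlations | Stated power | With female term | Without female term |
|---|---|---|---|
| Small | 90% | 88.1% | 90.7% |
| Medium | 86% | 85.3% | 88.3% |
| Large | 80% | 79.8% | 83.3% |

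The planned model reproduces the stated power to within 2 points. With no selection and no true effect it is unbiased, with a mean estimate of 0.01 points and 4.7% rejection.

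**2. Why cluster and period terms do not help.** Write the expected proportion in hospital i, period j as a_i + b_j + θT, where T = 1 for dual cement. If selection lowers the risk by δ in control periods, the expectation becomes a_i + b_j + θT − δ(1 − T) = (a_i − δ) + b_j + (θ + δ)T. The cluster terms absorb the constant, and the treatment coefficient becomes θ + δ. A benefit is a negative θ, so it shrinks by δ.

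**3. Size of δ.** The protocol gives no selection rate, so these inputs are assumptions: a share h = 0.5 of patients at high risk, risk ratio r = 2 or 3, and a fraction f = 0.1 or 0.3 of them absent from one arm's periods. With arm risk p, the low-risk patients have risk p₀ = p/(1 − h + hr). After selection the risk is

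p₀ × [(1 − h) + h(1 − f)r] / [(1 − h) + h(1 − f)].

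For p = 3%, r = 3, f = 0.3: p₀ = 0.015, and (0.5 × 0.015 + 0.35 × 0.045)/0.85 = 2.735%, so δ = 0.265 points. For p = 3%, r = 2, f = 0.1: p₀ = 0.02, and (0.5 × 0.02 + 0.45 × 0.04)/0.95 = 2.947%, so δ = 0.053. At p = 1.5% the shifts are half as large.

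| r, f | Control periods depleted: shift; estimate of a true 1.50 | Dual-cement periods depleted (1.5% risk): shift; estimate |
|---|---|---|
| 2, 10% | 0.053; 1.45 | 0.026; 1.53 |
| 3, 10% | 0.079; 1.42 | 0.039; 1.54 |
| 2, 30% | 0.176; 1.32 | 0.088; 1.59 |
| 3, 30% | 0.265; 1.24 | 0.132; 1.63 |

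With no true effect (3% in both arms), the shift is as in the first column, in either direction.

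**4. Consequence for the test.** Under the small correlations, lowering one arm's risk by 9% (about the last row) raises rejection under no effect from 4.7% to 7.9%. Power falls from 88% to 77% if control periods are depleted, and rises to 94% if dual-cement periods are.

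**5. What individual adjustment recovers.** I compared the planned model with a regression of observed minus expected proportions (15 hospitals, no correlation, 4,000 trials per scenario). Control periods are depleted by 30%. Results are rounded over repeated runs.

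| Scenario | Planned | Adjusted |
|---|---|---|
| r = 3, true 1.50 | about 1.24 points, 73–75% power | about 1.42 points, 87% power |
| r = 2, true 1.50 | 1.32 points, 78–79% power | about 1.44 points, 87% power |
| r = 3, no effect | about 0.26 points of apparent harm, 7–8% rejection | about 0, 4–5% rejection |
| No selection | 88–90% power | 91–92% power |

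The residual attenuation has a simple cause. Stage 1 omits treatment, so it corrects on the scale of the average risk, (3 + 1.5)/2 = 2.25%. For r = 3, f = 0.3 the correction is 0.265 × 2.25/3 = 0.199. With control periods depleted the adjusted estimate is 1.235 + 0.199 = 1.43. With dual-cement periods depleted it is 1.632 − 0.199 = 1.43. The error of about 0.07 compares with 0.265 and 0.132 unadjusted.

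**6. Power with no selection.** Removing the aggregate female term alone gives 90.7 − 88.1 = 2.6, 88.3 − 85.3 = 3.0 and 83.3 − 79.8 = 3.5 points in step 1. The 2–3 points seen in step 5 are of the same size, so they come from dropping that term (12 to 13 residual degrees of freedom), not from the risk adjustment.

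**The case against.** The strongest reply is that the plan already guards against selection. All registered eligible patients enter, there is no consent step at which to lose them, and analysis follows site allocation, so using the other cement does not move a patient between groups. Cluster and period terms remove stable hospital differences and common trends. All of this stands, and it narrows the route considerably. But these safeguards act once a patient has been judged a hemiarthroplasty candidate, or act on differences unrelated to treatment. They do not reach an eligibility judgement that changes with the cement.

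Second, supplementary analyses and baseline comparisons usually belong in the statistical analysis plan, which is not at hand and may contain them. This is right for the checks on inclusion, which are recommended here and not called missing. It does not apply to the primary model, because section 7.1 itself fixes its covariates. The adjusted Cox models in section 6.1 name no covariates, so they do not settle the matter.

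Third, a reader might infer from section 3.1 that patients do cross the line, because two thirds of the target group receive a cemented hemiarthroplasty. The document does not say why the others do not, and the figure is no evidence of borderline cases. Likewise, the remark there that inclusion is by department may simply describe cluster-level inclusion.

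Fourth, the simulation gives stage 1 the exact driver of selection, so recovery in practice will be less complete. That also stands.

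**Conclusion.** The point holds as a vulnerability, not as a demonstrated bias. Open allocation and local eligibility make differential inclusion possible, and the primary model would not correct it because its only patient-mix term is the cluster-period proportion of females. A reader might go further and conclude that the treatment effect is biased. The protocol does not support that: nothing in it shows that selection occurs, and neither direction nor size can be derived from it.

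Under the assumed inputs the shift is about 0.03–0.08 points at 10% selection and reaches 0.27 points at 30%, against a target difference of 1.5. The upper end requires the same selection in all 15 hospitals and a threefold risk. Because better adjustment is available from data already collected and costs no power, the change should be made.

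**What to change.** **Primary model (section 7.1).** Replace the aggregate proportion-of-females term by two-stage adjustment:
- Stage 1: a logistic model for infection on individual age, sex, ASA grade and, where available, BMI, without treatment. It gives the expected proportion in each cluster period.
- Stage 2: the existing linear regression, applied to observed minus expected proportions, on treatment, cluster and period.

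If the sponsor prefers to keep the current primary model, name this as a pre-specified sensitivity analysis.

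**Check on inclusion.** Fit the same cluster-period model, with treatment, cluster and period, to (a) the share of displaced fractures registered in the Swedish Fracture Register, at age 60 or over, that enter the trial, and (b) the ASA III–IV share and mean age of those included. State in advance that a difference by allocated cement will be reported as evidence of selection.

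**Cost.** Wording and modest programming. The patient variables are already registered, and check (a) needs only aggregate counts of registered fractures. Missing ASA grade or BMI needs a stated rule, only measured selection is removed, and the slight attenuation shown above remains. No change to who is offered a hemiarthroplasty is implied.

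### The pooled subgroup model gives both subgroups the same standard error, so with an uneven split and similar risks the subgroup CIs are too narrow for the smaller subgroup and too wide for the larger

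*Protocol*

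**What the plan says.** Protocol section 7.1 plans subgroup analyses of all event outcomes by sex, age, ASA class, stem type, head type and surgical approach. For categorical subgroups the contrast is estimated "using a linear model at the cluster level, with proportions summarized by cluster period and subgroup indicator as dependent variable". The terms are treatment, cluster, period, subgroup and treatment-by-subgroup interaction. Results are "presented with nominal 95% CI for each subgroup and the interaction p-value".

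No weights, subgroup-specific residual variance or robust standard error are stated. The same section leaves the imputation details and the odds-ratio method to the SAP, but it writes this model out. It also says that analyses will account for the design so that type I error rates and confidence intervals are correct.

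**The concern.** The sampling variance of a proportion is inversely related to the number of patients behind it. Hospital volumes in section 7 run from 32 to 294 operations a year, and each period lasts two years. A category holding 10% of patients has about 32 × 2 × 0.1 ≈ 6 patients per period in the smallest hospital. The complementary 90% has about 294 × 2 × 0.9 ≈ 529 in the largest. An ordinary linear model treats these two rows as equally precise. Its residual variance averages noisy and quiet cells, and that average is used for both subgroup CIs.

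At stake is how the published subgroup estimates are read. The smaller subgroup would look more certain than it is, and a real effect in the larger subgroup could be lost in an interval set mostly by the other subgroup's noise.

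**Working it through.** **Inputs from the protocol.** Two-sided 5% level: "The threshold of statistical significance will be set at a 2-sided p-value of 0.05". Control risk: "The 1-year risk of PJI in the included population is assumed to be 3% in the control group". Intervention risk: "Power was calculated under the hypothesis of 1.5% 1-year risk of PJI in the intervention group". Yearly volumes: "64, 132, 209, 294, 224, 97, 67, 144, 71, 45, 32, 94, 97, 112, and 65". They sum to 1,747, and 4 × 1,747 = 6,988, which agrees with "Hence the 4-year trial is assumed to include 7,000 patients in total". There are 15 hospitals, two periods and three correlation scenarios (0.01/0.008, 0.05/0.04, 0.1/0.08).

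**Assumed.** Subgroup shares, and (at first) the same risk and treatment effect in both subgroups. Correlations are taken on the latent logistic scale, the larger figure being the total and the smaller the part shared between periods. The female-proportion covariate is left out.

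**Step 1: reproduce the stated power.** The protocol's logit model was simulated and the primary cluster-period model fitted (30 rows, 17 parameters, 13 residual df).

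| Correlations | Protocol | Equal weights | Size weights |
|---|---|---|---|
| Small | 90% | 91.0% | 96.4% |
| Medium | 86% | 86.6% | 93.8% |
| Large | 80% | 78.6% | 87.2% |

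Only equal weighting reproduces the stated figures, so the aggregated linear model is read as unweighted.

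**Step 2: the expected distortion.** The subgroup model has 15 × 2 × 2 = 60 rows and 19 parameters (15 clusters, 1 period, 1 subgroup, 2 treatment contrasts), hence 41 residual df. Let f be the smaller subgroup's share. With similar risks and small correlations, cell variances are roughly proportional to 1/f and 1/(1−f). The pooled variance is their mean:

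½[1/f + 1/(1−f)] = 1/[2f(1−f)]

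The ratio of model SE to true SD is then √(1/[2(1−f)]) in the smaller subgroup and √(1/[2f]) in the larger. Approximate coverage is 2Φ(2.02 × ratio) − 1, where 2.02 is the 97.5% t quantile on 41 df.

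**Step 3: simulate the planned subgroup model** (small correlations; 10–32% rows combine several independent simulations). Each pair is smaller / larger subgroup.

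| Share f | SE/SD, formula | Coverage, formula | Coverage, simulated |
|---|---|---|---|
| 10% | 0.75 / 2.24 | 87% / 100% | 85–87% / 99.8–100% |
| 20% | 0.79 / 1.58 | 89% / 99.9% | 88–90% / over 99% |
| 32% | 0.86 / 1.25 | 92% / 99% | 91–92% / 98% |
| 40% | 0.91 / 1.12 | 93% / 98% | 92–94% / 97% |

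At a 50% split simulated coverage is about 95% / 94–95%. Large correlations give the same pattern: about 85–86% / 99.7% at a 10% share and 90% / 97% at 32%.

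**Step 4: precision.** Mean CI width in percentage points, small correlations. The pooled model gives both subgroups the same width.

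| Share f | Pooled, both | Separate, smaller | Separate, larger |
|---|---|---|---|
| 10% | 4.02 | 5.70 | 1.90 |
| 20% | 2.97 | 3.97 | 2.01 |
| 30% | 2.62 | 3.26 | 2.16 |
| 40% | 2.45 | 2.82 | 2.32 |

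At 10% the larger subgroup's CI excludes zero in about 23% of trials, against about 87–89% with separate unweighted fits. At 32% the figures are about 64–65% and 77%.

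**Step 5: unequal risks.** For a 35% subgroup, put [p(1−p) + (p/2)(1−p/2)]/share in place of 1/f and 1/(1−f), where p is the control risk:

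- 2.0% vs 3.54%: 0.084 vs 0.079, nearly equal; simulated coverage 95.1% / 95.4%.
- 1.5% vs 3.81%: 0.063 vs 0.085, reversed; 96.9% / 92.5%.
- 4.5% vs 2.19%: 0.186 vs 0.050, worse; 88.0% / 99.6%.

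**Step 6: interaction test and remedies.** The planned interaction test had type I error of 2.5–5.0% over shares of 10–40% and all three correlation scenarios. Separate unweighted fits covered about 93–96% in both subgroups in every scenario. Separate size-weighted fits fell to about 92–93% in the larger subgroup under large correlations.

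**The case against.** The strongest reply has four parts.

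- **The shares are not in the protocol.** This stands. Age or ASA class may split almost evenly, and then little is wrong. Uneven splits are plausible for stem, head and approach, where section 3.1 leaves surgeons wide choice, but this cannot be shown from the document.
- **The direction depends on risk.** This stands. A reader might infer that the smaller subgroup's CI is always too narrow. Step 5 shows that it need not be. Correct coverage then rests on two errors happening to cancel.
- **Homogeneity is judged by the interaction p-value.** This stands for the settings above. A reader might infer that the plan inflates false claims of subgroup differences, but the planned interaction test keeps its level there. One run outside these settings, with a 10% category strongly concentrated by hospital, gave 11.5%; that case was not pursued and is not part of this point.
- **The analyses are supportive, the CIs are called nominal, and a SAP is to follow.** This stands in part. A SAP could add separate variances without contradicting the protocol, and equal weighting is inferred from the primary model's power rather than stated for the subgroup model. But the protocol writes this model out instead of deferring it. Calling a CI nominal normally signals no multiplicity adjustment; it does not excuse 86% coverage.

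A reader might also credit the full power gain available at a 10% share (about 95% with separate size-weighted fits, from 23%) to correcting the variance. Part of that comes from size weighting, which is a separate choice. Separate variances alone give about 87–89%.

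**Conclusion.** The point holds for the subgroup-specific CIs when the split is uneven and event risks are similar. Under those conditions the planned 95% interval misses the truth in roughly 8–15% of trials for a smaller subgroup of 10–32%, while the larger subgroup's interval is wider than it need be, by a factor of about two at a 10% share (4.02 against 1.90 points). The distortion is moderate at about 30% and slight at 40–50%. These sizes rest on assumed shares, risks of 3% and 1.5%, and the protocol's own volumes and correlations.

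The primary analysis is not affected. The documents do not support a claim that the interaction test is invalid, or that every subgroup CI will be wrong. Because the remedy is cheap and section 7.1 sets correct CIs as its aim, the text is worth changing before database lock.

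**What to change.** In section 7.1, state that each subgroup's treatment contrast and CI come from the cluster-period linear model (treatment, cluster, period) fitted separately within that subgroup. Alternatively, keep one model but allow a separate residual variance per subgroup. Keep the equal cluster-period weighting that reproduces the primary analysis's stated power. Do not add size weights, because they bring back some undercoverage under the large-correlation scenario. The interaction test may stay as planned.

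The cost is a few lines of text. Residual df fall from 41 to 30 − 17 = 13 per subgroup, which raises the t multiplier from 2.02 to 2.16. The smaller subgroup's CI becomes wider, for example 5.70 instead of 4.02 points at a 10% share, which is its correct width.
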